During trial treatment, most variations in vital sign parameters, including heart rate, systolic and diastolic blood pressures, respiratory rate, and body temperature as well as body weight were small and the values remained stable and within the normal range. No obvious differences were observed among different dose cohorts. Overall, no clinically significant changes in blood pressure or heart rate were observed during trial treatment. The electrocardiograms (ECGs) in 5 of 13 subjects were normal at baseline. During trial treatment, none of the 5 subjects had abnormal ECGs assessed by the Investigator as clinically significant. Eight subjects had abnormal ECG findings at baseline. All these abnormal ECG findings were discussed at the Safety Monitoring Committee meetings and had no impact on the continuation of trial treatment.

Summary of safety

Overall, Avelumab was well tolerated up to 10 mg/kg, no DLT has been reported, and no safety concerns have been identified. The majority of the observed AEs were consistent with the subjects' underlying cancer disease.

3.I.3.B. Infusion-Related Reactions and Hypersensitivity

As of 23 January 2014, 7 subjects with infusion-related hypersensitivity have been reported in 119 subjects treated with Avelumab in the 2 Phase 1 trials, including 3 SAEs (2 infusion-related reactions, 1 anaphylactic reaction). Of the 3 SAEs, 2 were assessed by the Investigator as Grade 4 infusion-related reactions; however, review of the cases revealed that the described reactions fulfilled the criteria for Grade 2 infusion-related reactions. Follow-up with the Investigator is ongoing. The remaining 4 subjects were reported as having non-serious infusion-related reactions, including 3 subjects with Grade 2 and 1 subject with Grade 3 infusion-related reactions.

3.I.3.C. Pharmacokinetic and Pharmacodynamic Results

At the analysis cut-off date of 29 August 2013, 13 evaluable subjects were included for PK analysis. The PK profile of Avelumab at the highest dose level of 10 mg/kg (compared with the 1 and 3 mg/kg doses) is characterized by the following parameters:

- Average maximum concentration observed postdose (C_{max}) was 230.0 μ g/mL, with individual values ranging from 182.6 to 299.4 μ g/mL compared with 18.41 μ g/mL for the 1 mg/kg dose (14.49 to 22.64 μ g/mL) and 86.54 μ g/mL (76.89 to 101.1 μ g/mL) for the 3 mg/kg dose.
- Median time to reach C_{max} (t_{max}) was approximately 1 hour after the start of infusion for all doses.

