The period of monitoring for treatment-related toxicity will start with the first Avelumab infusion. All grade ≥ 3 CTCAE v.4.03 AEs will be recorded up to the last T cell or avelumab infusion. Beginning 4 weeks after the last study infusion, only study related toxicities will be collected per section 15. To evaluate for potential toxicities, patients will undergo a history and physical and, or laboratory evaluations (comprehensive chemistry panel and complete blood count) immediately prior to Avelumab infusion, prior to radiation therapy or intralesional IFN β -1B injection, immediately prior to infusions, days +1, +3, +7, +14, and +28 after each T cell infusion, and then as clinically indicated after the last infusion (for example, every 3 months for the first year, every 6 months for a year and then yearly see **Appendix B**). Clinical assessments at days +7, +14 and +28 after T-cell infusions may be performed by the patient's local provider and records assessed by the investigator within 14 days for any toxicities not previously assessed.

12.D. Efficacy Assessment

12.D.1. Clinical response by 'median time to new metastasis' (primary endpoint)

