Once the Avelumab infusion rate has been decreased by 50% or interrupted due to an infusion-related reaction, it must remain decreased for all subsequent infusions. If the subject has a second infusion-related reaction of Grade \geq 2 on the slower infusion rate, the infusion should be stopped and the subject should be removed from Avelumab treatment. If a subject experiences a Grade 3 or 4 infusion-related reaction at any time, the subject must discontinue Avelumab.

13.C.3. Management of severe hypersensitivity reactions and flu-like symptoms due to Avelumab infusions

If hypersensitivity reaction occurs, the subject must be treated according to the best available medical practice. Subjects should be instructed to report any delayed reactions to the Investigator immediately.

A. Symptoms

- Impaired airway
- Decreased oxygen saturation (< 92%)
- Confusion
- Lethargy
- Hypotension
- Pale / clammy skin
- Cyanosis

[figure not shown]
B. Management

1. Epinephrine injection and dexamethasone infusion
2. Patient should be placed on monitor immediately
3. Alert ICU for possible transfer if required

For prophylaxis of flu-like symptoms, 25 mg of indomethacin or comparable NSAID dose (for example, ibuprofen 600 mg, naproxen sodium 500 mg) may be administered 2 hours before and 8 hours after the start of each dose of Avelumab IV infusion. Alternative treatments for fever (for example, paracetamol) may be given to subjects at the discretion of the Investigator.

13.C.4. Tumor lysis syndrome

In addition, since Avelumab can induce antibody-dependent cell-mediated cytotoxicity (ADCC), there is a potential risk of tumor lysis syndrome. Should this occur, subjects should be treated per the local guidelines and the management algorithm below (**Figure 135**).⁷⁸

Definitions: TLS=tumor lysis syndrome

Figure 135. Assessment and initial management of tumor lysis syndrome
13.C.5. Delayed toxicities and immune-related adverse events (irAE) secondary to

Avelumab

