Patients will also be closely monitored for potential irAEs,^{79,80} which may manifest earliest after weeks of treatment. Such events may consist of persistent rash, diarrhea and colitis, autoimmune hepatitis, arthritis, glomerulonephritis, cardiomyopathy, or uveitis and other inflammatory eye conditions. The spectrum of hypothetical irAEs also includes formation of auto-antibodies like anti-nuclear antibodies (ANAs) or antineutrophil cytoplasmic antibodies (ANCAs). IrAEs will be managed according to **Section 13.E** with steroids.

Suggested management for Grade 2 adverse drug reactions (ADR):

- If a Grade 2 ADR resolves to Grade ≤ 1 by the last day of the current cycle, treatment may continue.
- If a Grade 2 ADR does not resolve to Grade ≤ 1 by the last day of the current cycle, infusions should not be given on the following cycle. If at the end of the following cycle the event has not resolved to Grade 1, the subject should permanently discontinue treatment with a Avelumab ADR (except for hormone insufficiencies, that can be managed by replacement therapy; for these hormone insufficiencies, up to 2 subsequent doses may be omitted).
- Upon the second occurrence of the same Grade 2 ADR (except for hormone insufficiencies that can be managed by replacement therapy) in the same subject, treatment with Avelumab must be permanently discontinued.

13.D. Management of Symptoms During T-Cell Infusion

Immediate reaction to infusion (i.e. defined as those occurring either during the first 24 hours following T-cell infusion) may occur due to release of cytokines from T cells stimulated by the recognition of targets. Mild transient symptoms have been observed with lymphokine-activated killer cell (LAK) and TIL cell infusions, and with infusions of antigen-specific T-cell clones (**FHCRC Protocol 2140**).

13.D.1. Milder reactions (i.e. <Grade 3 CTCAE v.4 or less severe than specified below) would include symptoms such as:

- Fever, chills, fatigue.
- Dyspnea, chest tightness, or myalgia,
- Alteration in vital signs such as:
 - Lowering of blood pressure, but with systolic BP ≥ 90 mm Hg, or ≤ 20 mm Hg below baseline.
 - Tachycardia, but with HR ≤ 130 or ≤ 30 above baseline.
 - Tachypnea, but with RR $\leq 32/\text{min}$ or ≤ 10 above baseline.
 - Hypoxemia, but O₂ saturation $\geq 88\%$ on room air, or $\leq 5\%$ fall from baseline.
 - Skin changes such as erythema, urticaria, or other rash.

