15. GUIDELINES FOR ADVERSE EVENTS REPORTING

15.A. Reporting of Adverse Events

All unexpected and serious AEs which may be due to study treatment or intervention must be reported to the FHCRC Institutional Review Office (IRO) per their current reporting requirements.

All grade ≥ 3 CTCAE v.4 AEs will be collected through 4 weeks after the last T-cell infusion and per section 12.C. Beginning 4 weeks after the last study infusion, only study related toxicities will be collected.

All SAEs that are unexpected and related to study treatment will be reported to the FDA on a MedWatch 3500 reporting form that will be submitted to the FDA within 15 calendar days. The reports will include the date and time of onset, severity and duration of the event, the relationship to study treatment, the treatment given, and the eventual outcome.

15.B. Definitions

Definitions associated with reportable events can be found on the FHCRC IRO extranet website. (Relevant FHCRC policies include, but are not limited the documents listed **[Table 6]**. Please also refer to the FHCRC IRO website.)

Table 6. FHCRC IRB policies for reportable events

IRB Policy 2.6	Adverse Events and Other Unanticipated Problems Involving Risks to Subjects or Others	http://extranet.fhcrc.org/EN/sections/iro/irb/ae.html
IRB Policy 1.9	Noncompliance with the Office of the Director's Human Research Protection Program Policy	http://extranet.fhcrc.org/EN/sections/iro/irb/ae.html
IRB Policy 1.1	Reporting Obligations for Principal Investigators	http://extranet.fhcrc.org/EN/sections/iro/irb/policy/index.html
IRB Policy 2.2	Continuing Review	http://extranet.fhcrc.org/EN/sections/iro/irb/policy/index.html
IRB Policy 1.13	Investigational New Drugs (IND), Biologics and Investigational Device Exemptions (IDE)	http://extranet.fhcrc.org/EN/sections/iro/irb/policy/index.html

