All members have experience in the management of patients with skin cancers and in the conduct and monitoring of clinical trials. Any DSMB member who has or develops a significant conflict of interest will be required to resign from the DSMB. DSMB membership is for the duration of the clinical trial. If any members leave the DSMB during the course of the trial, the PI will promptly appoint their replacement.

A monitor will be retained to monitor study progress. The scope of monitoring will be based on the FHCRC/UW Data and Safety Monitoring Plan (DSMP): <http://www.cancerconsortium.org/rto/prr/DSMPlan.pdf>. Per the DSMP, an initial monitoring visit is expected after the first 4 patients have received treatment with 100% of records verification. Monitoring reports will be forwarded to the DSMB, the IND sponsor, and the PI at FHCRC.

Content of Reports for the DSMB:

- Study number and title. Brief summary of the study design
- Protocol amendments
- Status of accrual. If accrual is slower than expected, a plan for increasing enrollment
- Compliance
- Analyses of primary and secondary endpoints
- Analyses of AEs and overall safety data. A listing of SAEs by subject and by body system
- Analysis of lab values

DSMB Meeting Minutes

The CTSO will provide staff to assist with minutes for the DSMB meeting. The FHCRC IRB and Regulatory Affairs Manager will be included on the distribution list. At the time of IRB annual renewal, DSMB minutes will be required, if not already provided.

Statistical Monitoring Guidelines

The DSMB will review all Grade 3 or greater toxicities as defined by version 4.0 of NCI Common Toxicity Criteria and determine whether the study should be prematurely discontinued due to toxicity. Toxicity grading will be evaluated by the clinical investigators. Criteria for discontinuing of therapy in an individual patient are described in protocol section titled "Management of Toxicities and Complications". Criteria for discontinuing the trial is described in section titled "Data and Safety Monitoring".

The type and grade of toxicities noted during therapy will be summarized for each dose level. All AEs noted by the investigator will be tabulated according to the affected body system. Descriptive statistics will be used to summarize changes from baseline in clinical laboratory parameters. Tumor responses will be determined as specified above.

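### Routine adverse event collection during treatment starts at Grade 3, but avelumab is slowed, withheld or permanently stopped on Grade 1-2 reactions that no section requires to be recorded as graded events

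*Combined protocol and SAP*

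**What the plan says.** **Collection.** Section 12.C: "All grade ≥ 3 CTCAE v.4.03 AEs will be recorded up to the last T cell or avelumab infusion". Section 15.A: "All grade ≥ 3 CTCAE v.4 AEs will be collected through 4 weeks after the last T-cell infusion". The two sections end the window differently, which is a separate matter, but both set the same Grade 3 floor. From 4 weeks after the last study infusion, both limit collection to study-related toxicities and state no grade floor.

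**Dosing rules for avelumab.** Under 13.C.2 (Table 5), a Grade 1 infusion reaction halves the rate. A Grade 2 reaction stops the infusion, which then resumes at half rate. After either, the rate is fixed: "it must remain decreased for all subsequent infusions". A second reaction of Grade 2 or higher at the slower rate removes the patient from avelumab. Under 13.C.5, an unresolved Grade 2 reaction means that the next cycle is withheld and, if it still persists, that avelumab ends permanently. Avelumab also ends "Upon the second occurrence of the same Grade 2 ADR". Hormone insufficiencies that can be replaced are treated differently in both cases. Section 13.G lists repetitive related Grade 2 reactions as a reason to leave the study.

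**Endpoint and reporting.** Primary objective 1 is to assess and compare toxicity between the groups, and primary endpoint 1 (5.A) carries no grade limit. Section 13.B defines excessive toxicity as a new Grade 3 or higher event, with listed exceptions. Section 18 takes its definition of toxicity from Section 13 as a whole. Section 16.C promises a summary by type and grade, and adds: "All AEs noted by the investigator will be tabulated according to the affected body system".

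**The concern.** The floor for collecting events sits above the level at which the plan acts on them. A patient can have a dose slowed, a cycle withheld or avelumab ended because of Grade 2 toxicity without any section requiring that event to be entered with a grade, an onset date and an attribution. The rule on a second occurrence also depends on a first occurrence that need not be in the data set, so adherence to the rule cannot be checked from the data.

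The comparison of toxicity between groups is a primary objective. If Grade 2 events that alter treatment are not captured in the same way in both groups, the Grade 3+ table will describe tolerability incompletely, and the tables promised in 16.C will lack their lower grades. Reactions to T-cell infusion below Grade 3, which 13.D.1 manages by slowing the infusion or by supportive care, fall under the same floor and arise only in Group 2.

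**Working it through.** **1. Rules against records**

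| Trigger | Consequence | Record required |
|---|---|---|
| Grade 1 infusion reaction (13.C.2) | Rate halved, kept for later infusions | None as a graded event |
| First Grade 2 infusion reaction (13.C.2) | Interrupted, resumed at half rate | None as a graded event |
| Second Grade 2 infusion reaction at the slower rate (13.C.2) | Removed from avelumab | Stop reason only (13.G) |
| Grade 2 reaction unresolved at end of cycle (13.C.5) | Next cycle withheld | None as a graded event |
| Grade 2 reaction still unresolved a cycle later, or the same one recurring (13.C.5) | Avelumab ended | Stop reason only (13.G) |
| Repetitive related Grade 2 reactions (13.G) | Off study | Stop reason only (13.G) |

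The table concerns non-serious events. Serious ones have their own route: 16.C sends them to the DSMB whatever their grade.

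**2. Do these events enter the toxicity rate?** Under 13.B they do not, because its threshold is Grade 3. Section 18, however, points to all of Section 13, which also holds the Grade 2 rules, and the exceptions in 13.B.1 include two Grade 2 events that could never have met a Grade 3 threshold. The text therefore leaves the answer open.

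**3. The plan's own operating figures.** Section 18 suspends a group at 2 of 2-3, 3 of 4-5, 4 of 6-8 or 5 of 9-10 toxicities. It states suspension probabilities of about 0.03 and 0.76 at true rates of 10% and 50%. With checks after every patient, the recursion is f_n(k) = (1-p)·f_{n-1}(k) + p·f_{n-1}(k-1), removing k at or above the limit. Crossings by patients 3, 5, 8 and 10 add up as follows:

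- p = 0.10: 0.0280 + 0.0024 + 0.0018 + 0.0002 = 0.0324
- p = 0.50: 0.5000 + 0.0938 + 0.1289 + 0.0361 = 0.7588

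The first term is P(2 or more of 3); at 10% it is 3 × 0.1² × 0.9 + 0.1³ = 0.028. Both stated figures are reproduced.

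**4. Would counting the Grade 2 stops matter?** The documents give no rate for them, so the following is assumption. Let a further share d of patients stop on a Grade 2 event without a Grade 3+ toxicity, and apply the same rule at p + d.

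| d | Suspension, Grade 3+ rate 10% | Suspension, Grade 3+ rate 20% | At least 1 such stop in 10: 1-(1-d)^10 |
|---|---|---|---|
| 0 | 0.032 | 0.141 | 0 |
| 2.5% | 0.052 | 0.182 | 22% |
| 5% | 0.077 | 0.226 | 40% |
| 10% | 0.141 | 0.327 | 65% |
| 20% | 0.327 | 0.552 | 89% |

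If the events are recorded and reported separately, the d = 0 row stands and nothing in Section 18 moves.

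**5. Where known reactions fall relative to the floor.** Section 3.I.3.B reports 7 infusion-related hypersensitivity cases in 119 subjects (5.9%):

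- 4 non-serious: 3 Grade 2 and 1 Grade 3.
- 3 serious: 1 anaphylactic reaction with no grade given, and 2 infusion reactions that the investigator graded 4. On review of these two, "the described reactions fulfilled the criteria for Grade 2 infusion-related reactions", with follow-up still open.

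The secure count of non-serious Grade 2 reactions is 3/7 = 43%, or 3/119 = 2.5% of those treated. Accepting both regradings gives (3 + 2)/7 = 71%, or 5/119 = 4.2%.

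**The case against.** The best defence is that the plan is not blind below Grade 3. Section 13.G requires the reason for premature discontinuation on the case report form, without a grade limit. Serious events reach the DSMB at any grade. Late study-related toxicities carry no grade floor. The 16.C tabulation of all noted events can be read as provision for lower grades. So a reader who infers that only Grade 3+ events are collected, or that patients could leave treatment for toxicity with no trace in the data, goes beyond the documents.

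That much stands, but it does not close the gap. A stop reason need not carry grade, onset or attribution, and it covers neither rate reductions, nor withheld cycles, nor the first Grade 2 event. Non-serious Grade 2 events are not in the serious event listing. The late rule begins 4 weeks after the last infusion, after every dosing decision. The 16.C sentence says what will be tabulated; it does not tell sites what to collect.

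Three further inferences are tempting and not supported:

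- That the floor would miss 5 of 7 known reactions. Two of the five were serious and graded 4 by the investigator. Section 16.C leaves grading in this trial to the clinical investigators, so as graded those two would have passed the floor, and they would reach the DSMB in any case.
- That these counts show treatment-ending toxicity. A first Grade 2 infusion reaction leads to resumption at half rate.
- That Grade 2 events are the expected signal of adding T cells. The documents describe mild transient symptoms with earlier cell infusions and call delayed T-cell toxicity unlikely.

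The Grade 3 threshold for suspension also has a stated basis: the 30% limit is set against Grade 3+ rates of roughly 30% to 40% with platinum-based chemotherapy. That supports leaving the rule alone. It does not support leaving the lower-grade events unrecorded.

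**Conclusion.** The mismatch holds. During treatment, non-serious Grade 1-2 events that change or end avelumab dosing need not be recorded as graded, attributed adverse events, and a treatment-ending one need appear only as a stop reason. They lie outside a toxicity rate built on 13.B, and the 16.C tables cannot be filled from Grade 3+ data.

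A reader might go further and call these events missing from the primary safety endpoint. That is firm only for the 13.B-based rate: endpoint 5.A.1 has no grade limit, and Section 18 refers to Section 13 as a whole.

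The size can be given only as an indication. In the avelumab phase 1 experience, 3 of 7 infusion reactions were non-serious Grade 2, or 5 of 7 Grade 2 if the open regradings are accepted. How often Grade 2 events end treatment is not stated. The conclusion assumes that the case report form, which is not in the documents, follows the protocol text and asks for no more.

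**What to change.** - **12.C and 15.A:** beside Grade 3+ events, collect with grade, onset and attribution (a) any adverse event of any grade that slows, interrupts, delays, withholds or stops a study treatment, (b) all infusion and cytokine reactions, and (c) treatment-related Grade 2 events.
- **16.C:** report toxicity leading to modification or discontinuation of treatment, by group, beside the Grade 3+ table. With 10 non-randomised patients per group the comparison is descriptive.
- **Section 18:** state that toxicity for the 30% limit means the 13.B definition, and that the added events are reported separately and do not count toward suspension. The stated 0.03 and 0.76 then stand.

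The cost is protocol wording and a few extra case report form lines per patient in 20 patients. Most of this information should already be in the chart, since the dosing rules depend on it. No dosing or stopping rule changes.

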- At Day 15 before the second dose administration, an average minimum postdose (trough) concentration (C_{min}) of 17.14 μ g/mL was observed for the subjects who received a dose of 10 mg/kg with individual values ranging from 11.72 to 26.87 μ g/mL compared with 0.23 μ g/mL for the 3 subjects treated at a 1 mg/kg dose

(0 to 0.68 $\mu\text{g}/\text{mL}$) and 5.66 $\mu\text{g}/\text{mL}$ (4.56 to 6.99 $\mu\text{g}/\text{mL}$) for the 3 subjects treated at a 3 mg/kg dose.

- The average area under the concentration-time curve (AUC_{tau}) for the first infusion was 23485 $\mu\text{g}/\text{mL}\cdot\text{h}$ (16439 to 29316 $\mu\text{g}/\text{mL}\cdot\text{h}$) compared with 1286 $\mu\text{g}/\text{mL}\cdot\text{h}$ for the 1 mg/kg dose (854 to 1669 $\mu\text{g}/\text{mL}\cdot\text{h}$) and 8067 $\mu\text{g}/\text{mL}\cdot\text{h}$ (7516 to 8485 $\mu\text{g}/\text{mL}\cdot\text{h}$) for the 3 mg/kg dose.
- Interindividual variability in exposure parameters (C_{max} and AUC_{tau}) was low. In the 10 mg/kg cohort, the coefficient of variation for the geometric mean was 19.1% for C_{max} and 21.9% for AUC_{tau} .
- No significant accumulation of drug concentrations was recorded in all dose levels. After the first infusion, trough levels did not fall beyond the lower limit of detection, but were very low (C_{min}). Based on the limited number of PK data available after the second infusion, it was concluded that these residual trough values did not increase up to the fourth infusion. The peak values also remained at a similar level over time.
- Half-life ($t_{1/2}$) was 92.8 hours (77.2 to 117.4 hours) compared with 63.4 hours for the 1 mg/kg dose (45.9 to 85.6 hours) and 91.3 hours (88.5 to 95.1 hours) for the 3 mg/kg dose.

From the PK perspective, no unexpected observations or findings that would raise safety concerns could be identified. The shift to a longer $t_{1/2}$ from 1 to 3 mg/kg doses is consistent with a progressing target occupancy, which indicated that the fast target-mediated clearance reached to a saturated stage, while a slow unspecific elimination became prominent. Similar half-lives for the 3 and 10 mg/kg doses indicated that the target-mediated clearance was nearly saturated by the 3 mg/kg dose. The PK parameters determined, support a DLT evaluation period of 21 days, which covered approximately 5 half-lives.

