Management will be by **decreasing the rate of infusion and/or appropriate supportive care** such as:

- Acetaminophen or Demerol for fever and chills. (All subjects who develop fever or chills should have a blood culture drawn).
- Acetaminophen for headache.
- Diphenhydramine for nausea and vomiting.
- Fluid administration for hypotension.
- Supplemental oxygen for hypoxemia.

13.D.2. More severe reactions occurring during the 1-2 hour infusion would include symptoms such as:

- Hypotension with systolic BP <90 mm Hg and >20 mm Hg below baseline
- Tachycardia with HR >130 and >30 above baseline.
- Tachypnea with RR >32 and >10 above baseline.
- Hypoxemia with O₂ saturation of <88% and >5% fall from baseline.

Management will be by **terminating the infusion and administering supportive medical care**.

- If patient responds to supportive care by normalization of vital signs or resolution of hypoxemia and PI deems it safe to continue, the infusion will be restarted at slower rate.
- If the patient does not respond by normalization of vital signs or hypoxemia after supportive care alone, **methylprednisolone to ablate the infused T cells will be administered as per Section 13.E.**

13.D.3. Any unexpected severe toxicity (see Section 13.B) occurring in the first 24 hours (due to the T-cell infusion and not attributable to a non-infusion-related cause).

Management will be by **supportive medical care and methylprednisolone will be administered as per Section 13.E.**

13.D.4. Delayed toxicities secondary to T-cell infusions

Although unlikely, it remains possible that the infusion of MCPyV TAg-specific T cells will result in delayed toxicities related to the recognition of tumor tissue. It is anticipated that the symptoms and signs will occur within hours to four weeks after completion of the T-cell infusion.

Any toxicities requiring treatment discontinuation (see Section 13.B) occurring within 4 weeks of study treatment (potentially due to the T-cell infusion and not attributable to a non-infusion-related cause) **will be managed by supportive care and MP will be administered as per Section 13.E.**

13.E. Management of Severe Treatment-related Toxicities with Corticosteroids

- i. The patient will receive corticosteroids if treatment-related toxicity warranting ablation of T cells is observed.
- ii. The patient will be hospitalized for the first 48 hours for monitoring. The following dose schedule is recommended:

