Day 1	Intravenous Methylprednisolone at 2 mg/kg
Day 2	Intravenous Methylprednisolone at 2 mg/kg
Day 3-4	Prednisone at 30 mg po b.i.d.
Day 5-6	Prednisone at 15 mg po b.i.d.
Day 7-8	Prednisone at 10 mg po b.i.d.
Day 9-10	Prednisone at 10 mg po q.d
Day11-12	Prednisone at 5 mg po q.d.

- iii. The *in vivo* frequency of infused CD8⁺ T cells will be assayed immediately prior to and between 48 and 72 hours after the start of steroid therapy.

13.F. Concomitant Therapy

13.F.1. As with all monoclonal antibody therapies, Avelumab carries a risk of allergic reaction. Avelumab will be administered at the SCCA in a setting that allows for immediate access and administration of therapy for severe allergic or hypersensitivity reactions, such as the ability to implement immediate resuscitation measures. Steroids (dexamethasone 10 mg), epinephrine (1:1000 dilution), allergy medications (antihistamines), or equivalents are available for immediate access. If hypersensitivity reaction occurs, the subject must be treated according to the best available medical practice.

13.F.2. Subjects will be pretreated with H1 blockers (diphenhydramine 25-50 mg PO or IV, or equivalent), and acetaminophen 500 to 650 mg (orally), 30 to 60 minutes prior to each Avelumab and T-cell infusion.

13.F.3. Any medications (other than those excluded by the clinical trial protocol) that are considered necessary for the subjects' welfare and will not interfere with the IMP may be given at the Investigator's discretion. For example, active infections occurring after initiating the study should be treated according to the standard of care. Other agents might include analgesics, antinausea medications, antihistamines, diuretics, anti-anxiety medications, and medication for pain management, including narcotic agents.

13.F.4. The following agents are not allowed while on study:

- Systemic corticosteroids (except as outlined for management of toxicity of Avelumab and non-transduced CTL)
- Immunotherapy (for example, interleukins, MCC vaccines, intravenous immunoglobulin, expanded polyclonal TIL or LAK therapy)
- Pentoxifylline, other small-molecule or chemotherapy cancer treatment
- Other investigational agents
- Any vaccine therapies for the prevention of infectious disease (for example, seasonal flu vaccine, human papilloma virus vaccine) except administration of the inactive influenza vaccine

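### Section 13.C.5 manages avelumab immune-related events through 13.E, whose only steroid schedule is a fixed 12-day course written to ablate infused T cells, with no link to resolution and no relapse rule

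*Combined protocol and SAP*

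**What the plan says.** Section 13.B stops study treatment for excessive toxicity, broadly a new Grade 3 or higher event outside the listed exceptions. It allows corticosteroids where clinically indicated and points to 13.C. Within 13.C, subsection 13.C.5 covers delayed and immune-related toxicity of avelumab and names colitis, autoimmune hepatitis, glomerulonephritis and cardiomyopathy among the possibilities. Its steroid instruction is one sentence, beginning "IrAEs will be managed according to" and pointing to Section 13.E.

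Section 13.E has three items:

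- **Trigger:** "The patient will receive corticosteroids if treatment-related toxicity warranting ablation of T cells is observed".
- **Schedule:** 48 hours in hospital, then "The following dose schedule is recommended": methylprednisolone 2 mg/kg on days 1 and 2; prednisone 30 mg twice daily on days 3-4, 15 mg twice daily on days 5-6, 10 mg twice daily on days 7-8, 10 mg once daily on days 9-10 and 5 mg once daily on days 11-12.
- **Monitoring:** the frequency of infused CD8+ T cells "will be assayed immediately prior to and between 48 and 72 hours after the start of steroid therapy".

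Section 13.D.2 states the purpose for infusion reactions: "methylprednisolone to ablate the infused T cells will be administered as per Section 13.E". Section 13.F.4 bars systemic corticosteroids on study apart from uses the protocol outlines for avelumab or T-cell toxicity.

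**The concern.** The schedule and the event do not match. Trigger, purpose and monitoring in 13.E all concern infused T cells. Group 1 has none, so item iii cannot be carried out there and the trigger has no meaning, yet 13.E is the only steroid guidance in the protocol text for an irAE in that group. In Group 2 an irAE may come from avelumab, which steroids do not clear.

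The step-down is by date. No line asks for improvement before the dose falls, and none says what to do if the event returns. The protocol does tie action to resolution elsewhere: for re-dosing after a Grade 2 reaction, 13.C.5 says "If at the end of the following cycle the event has not resolved to Grade 1, the subject should permanently discontinue treatment". That rule governs avelumab and not steroids, but it shows that an event is expected to be able to outlast a 14-day cycle.

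At stake is a patient with, say, Grade 3 colitis or hepatitis who is treated as recommended. The dose falls sharply after 48 hours and reaches zero after day 12, whatever the state of the event, possibly while PD-L1 is still blocked.

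**Working it through.** **Inputs (Section 3.I.3.C, 10 mg/kg, the dose used here).** Mean Cmax is 230.0 µg/mL. The Day 15 pre-dose trough averages 17.14 µg/mL, a figure that "was observed for the subjects who received a dose of 10 mg/kg with individual values ranging from 11.72 to 26.87" µg/mL. The half-life "was 92.8 hours (77.2 to 117.4 hours) compared with 63.4 hours for the 1 mg/kg dose"; the 1 mg/kg range is 45.9 to 85.6 h. Occupancy was near complete above 0.2 µg/mL in assay validation. It exceeded 90% in all subjects at the 3 mg/kg Day 15 troughs, of which the lowest was 4.56 µg/mL. No significant accumulation was seen, so first-dose values are used for later cycles.

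**The plan's own figure first.** The protocol says 21 days covers about 5 half-lives. 5 × 92.8 / 24 = 19.3 days, and 21 × 24 / 92.8 = 5.4 half-lives, so the statement reproduces.

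**Check of first-order decline.** 230.0 × 0.5^(336/92.8) = 18.7 µg/mL, against 17.14 observed.

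**Model.** Days are counted from the last infusion, with no further infusion. The protocol describes faster, target-mediated clearance at low concentration, so the decline uses 92.8 h down to 4.56 µg/mL and 63.4 h below that.

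- 4.56 µg/mL is reached at 14 + log2(17.14/4.56) × 92.8/24 = 14 + 1.910 × 92.8/24 = day 21.4.
- 0.2 µg/mL is reached at 21.4 + log2(4.56/0.2) × 63.4/24 = 21.4 + 4.511 × 63.4/24 = day 33.3.
- A course started on day s ends on day s + 12. Gap = day the level is reached − (s + 12).

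| Steroid start | Course ends | Avelumab at course end | Multiple of 0.2 | Gap to 0.2 µg/mL | Gap to 4.56 µg/mL |
|---|---|---|---|---|---|
| day 0 | day 12 | 24.5 µg/mL | 123 | 21.3 days | 9.4 days |
| day 7 | day 19 | 7.0 µg/mL | 35 | 14.3 days | 2.4 days |
| day 14 | day 26 | 1.36 µg/mL | 6.8 | 7.3 days | none |

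The levels are 17.14 × 0.5^((12−14)×24/92.8) = 24.5; 17.14 × 0.5^((19−14)×24/92.8) = 7.0; and 4.56 × 0.5^((26−21.4)×24/63.4) = 1.36.

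**Sensitivity for the 0.2 µg/mL gap.**

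- Two-phase, low values (11.72 µg/mL; 77.2 h then 45.9 h): 0.2 is reached on day 27.0, gap 1 to 15 days.
- Two-phase, high values (26.87 µg/mL; 117.4 h then 85.6 h): day 42.6, gap about 17 to 31 days.
- Single half-life of 92.8 h: day 38.8, gap 12.8 to 26.8 days.
- Single half-life, high values (26.87 µg/mL, 117.4 h): gap 22.6 to 36.6 days, or up to 5.2 weeks.
- Fastest corner (11.72 µg/mL, 45.9 h throughout): −0.8 days for a day-14 start, so no gap.

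**Step in dose.** At 80 kg, methylprednisolone is 160 mg/day on days 1-2 and prednisone 60 mg/day on days 3-4. Assuming 4 mg of methylprednisolone equals 5 mg of prednisone (not a figure from the documents), this is 200 to 60 mg, a 70% drop; it is 60% at 60 kg and 76% at 100 kg.

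**The case against.** The heading of 13.E is general, its schedule is recommended and not required, 13.B leaves steroids to clinical indication, and 13.F.4 excepts avelumab toxicity. A clinician may go longer. Study treatment has already stopped, related toxicities are still collected, and a multidisciplinary team follows the patient. All of this stands and limits the size of the point. It does not remove it: 13.E is the only irAE steroid guidance in the protocol text, and 13.F.4 ties permitted steroid use to what is outlined. The Investigator's Brochure (Appendix C) and the cited paper on irAE management were not available; they may say more, but 13.C.5 sends the reader to 13.E for steroids.

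Three stronger readings are tempting and are not supported.

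- A reader might infer that the protocol itself gives a period of blockade beyond the course. It does not. The gap is derived, and it depends on when steroids start and on a threshold measured on blood cells. The protocol's choice of 10 mg/kg allows for differences between blood and tumor. With a single 92.8 h half-life there is no gap if steroids start more than about 27 days after the last infusion.
- A reader might infer that steroids must outlast occupancy, or that relapse after day 12 is likely. No document says either.
- In the other direction, the 5-half-life yardstick (19.3 days) would suggest no gap for a day-14 start, which ends on day 26. But 230.0/2^5 = 7.2 µg/mL remains at five half-lives, above the 4.56 µg/mL at which occupancy over 90% was observed. It does not mark the end of blockade.

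**Conclusion.** The point holds as a mismatch of purpose, and the amendment should be made. A fixed course built to remove infused T cells is the only recommended treatment for avelumab irAEs in both groups; it tapers by date and does not address recurrence. That conclusion comes from the text and does not depend on the pharmacokinetics.

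The pharmacokinetics show the direction. On average values, with a start within 14 days of the last infusion, the course ends above 0.2 µg/mL. The gap is about 1 to 3 weeks on the two-phase decline, about 0 to 5 weeks across the reported ranges, and 9, 2 or 0 days on the stricter 4.56 µg/mL level. This assumes first-order decline within each phase, no further infusion, and that occupancy on circulating cells stands for tissue. The clinical effect of the gap cannot be sized from these documents, and the sections available give no rate of Grade 3 or higher irAEs.

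**What to change.** One amendment of a few sentences:

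1. **13.E:** state that items i to iii and the 12-day schedule apply to T-cell infusion toxicity.
2. **13.C.5:** for Grade 3 or higher avelumab irAEs in either group, start steroids at the 13.E day 1-2 dose or as clinically indicated, and continue until Grade 1 or less. Then taper gradually, and return to the last effective dose if the event recurs. About 4 weeks of taper is suggested, with the exact length left to the investigator. That length is a judgement; it is not derived from the occupancy estimate and would not cover it in every case.
3. **13.B:** cite the new 13.C.5 text.
4. **13.F.4:** name that course as an outlined use of systemic corticosteroids.

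The Grade 2 rules stay as they are. No patients are added. The cost is longer steroid exposure and one or two extra clinic or telephone checks for the few patients affected. Little efficacy is lost, because 13.B has already stopped their study treatment and the first two days already use the T-cell-ablating dose.
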